Stomatitis	Mild discomfort	Painful, difficulty swallowing, but able to eat and drink	Painful: unable to swallow solids
Clinical symptom not otherwise specified in this table	No therapy; monitor condition	May require minimal intervention and monitoring	Requires medical care and possible hospitalization
Laboratory values not otherwise specified in this table	Abnormal, but requiring no immediate intervention; monitor	Sufficiently abnormal to require evaluation as to causality and perhaps mild therapeutic intervention, but not of sufficient severity to warrant immediate changes in study vaccine	Sufficiently severe to require evaluation and treatment, including at least temporary suspension of study vaccine

LABORATORY TOXICITY GRADING

Serum chemistry	Mild (Grade 1)	Moderate (Grade 2)	Severe (Grade 3)
Bilirubin (when accompanied by any increase in other liver tests)	1.1-<1.25 x ULN	1.25-<1.5 x ULN	≥1.5 x ULN
Bilirubin (when other liver function tests are in normal range)	1.1-<1.5 x ULN	1.5-<2.0 x ULN	≥2.0 x ULN
AST	1.1-<2.0 x ULN	2.0-<3.0 x ULN	≥3.0 x ULN
ALT	1.1-<2.0 x ULN	2.0-<3.0 x ULN	≥3.0 x ULN
GGT	1.1-<2.0 x ULN	2.0-<3.0 x ULN	≥3.0 x ULN
Pancreatic amylase	1.1-1.4 x ULN	1.5-1.9 x ULN	≥2.0 x ULN
Uric acid	7.5-9.9 mg/dL	10-12.4 mg/dL	≥12.5 mg/dL
CK	See Neuromuscular Toxicity		
Creatinine 3 months – 2 years of age	0.6-0.8 x ULN	0.9-1.1 x ULN	≥1.2 x ULN
Creatinine 2 – 12 years of age	0.7-1.0 x ULN	1.1-1.6 x ULN	≥1.7 x ULN
Creatinine greater than 12 years of age	1.0-1.7 x ULN	1.8-2.4 x ULN	≥2.5 x ULN
Hypernatremia (mEq/L or mmol/L)	-	<145-149 mEq/L	≥150 mEq/L
Hyponatremia (mEq/L or mmol/L)	-	130-135 mEq/L	≤129 mEq/L
Hyperkalemia (mEq/L or mmol/L)	5.0-5.9 mEq/L	6.0-6.4 mEq/L	≥6.5 mEq/L
Hypokalemia (mEq/L or mmol/L)	3.0-3.5 mEq/L	2.5-2.9 mEq/L	≤2.4 mEq/L

Hypercalcemia	10.5-11.2 mg/dL	11.3-11.9 mg/dL	≥12.0 mg/dL
Hypocalcemia	7.8-8.4 mg/dL	7.0-7.7 mg/dL	≤6.9 mg/dL
Hypomagnesemia	1.2-1.4 mEq/L	0.9-1.1 mEq/L	≤0.8 mEq/L
Hyperglycemia	116-159 mg/dL	160-249 mg/dL	≥250 mg/dL
Hypoglycemia	55-65 mg/dL	40-54 mg/dL	≤39 mg/dL
Hematology	Mild (Grade 1)	Moderate (Grade 2)	Severe (Grade 3)
Hemoglobin for children greater than 3 months and less than 2 years of age	9.0-9.9 mg/dL	7.0-8.9 mg/dL	<7.0 mg/dL
Hemoglobin for children greater than 2 years of age	10.0-10.9 mg/dL	7.0-9.9 mg/dL	<7.0 mg/dL
Absolute neutrophil count	750-1200/mm ³	400-749/mm ³	≤399/mm ³
Platelets	-	50,000-75,000/mm ³	≤49,999/mm ³
PT	1.1-1.2 x ULN	1.3-1.5 x ULN	≥1.6 x ULN
PTT	1.1-1.6 x ULN	1.7-2.3 x ULN	≥2.4 x ULN
Urinalysis	Mild (Grade 1)	Moderate (Grade 2)	Severe (Grade 3)
Proteinuria	1+ or < 150 mg/day	2+ or 150-499 mg/day	3+ or ≥500 mg/day
Hematuria	Microscopic <25 cells/hpf	Microscopic >25 cells/hpf	-

RANGES TO CONVERT FDA SCALE TO SI UNITS (CHILDREN <12 YEARS)

Serum chemistry	Mild (Grade 1)	Moderate (Grade 2)	Severe (Grade 3)
Uric acid	446-589 μmol/L	590-738 μmol/L	>738 μmol/L
Hypernatremia	-	145-149 mmol/L	>149 mmol/L
Hyponatremia	-	130-135 mmol/L	<130 mmol/L
Hyperkalemia	5.0-5.9 mmol /L	6.0-6.4 mmol/L	>6.4 mmol/L
Hypokalemia	3.0-3.5 mmol /L	2.5-2.9 mmol/L	<2.5 mmol/L
Hypercalcemia	2.62-2.79 mmol/L	2.80-2.97 mmol/L	>2.97 mmol/L
Hypocalcemia	1.95-2.10 mmol/L	1.75-1.94 mmol/L	<1.75 mmol/L
Hypomagnesemia	0.60-0.70 mmol/L	0.45-0.59 mmol/L	<0.45 mmol/L
Hyperglycemia	6.44-8.83 mmol/L	8.84-13.82 mmol/L	>13.82 mmol/L
Hypoglycemia	3.05-3.61 mmol/L	2.22-3.04 mmol/L	<2.22 mmol/L

5. HEMOGLOBIN CUT-OFF VALUES

Where no institutional normal reference ranges is available for hemoglobin, the following cut-off values are proposed. It is imperative to note that there are no standard accepted normative values for hemoglobin in most African countries and therefore, the following recommendations are based on the review of several published sources and in consultation with the sites involved with the study. In the table below, 'simplified' means that the number of cut-off categories has been reduced to decrease complexity and facilitate understanding about eligibility. Similarly, 'adjusted for safety' means that the references may quote lower average or -2 SD values for hemoglobin but these values are considered to be too low for these subjects.

Group	Value (g/dL)		Reference	Outcome
Adult and HIV+	Male 12.1		Female 9.5 LLN value for local sites in Kenya and Uganda, current values being used in Phase 1	Values kept for consistency
Adolescent 16-18 yrs	Male 12.1		Female 9.5 Robins reference 10.4 g/dL for girls and 12.4 g/dL for boys	Values simplified to correspond to adult cut-offs
Adolescent 11-15 yrs	Male 11.0		Female 9.5 Robins reference 11.0 g/dL for girls and boys	Value adjusted down for boys, no change for girls
Children 6-10 yrs	11.0		Robins reference 10.7 g/dL for girls and boys	Value simplified
Children 2-5 yrs	11.0		Robins reference 10.4 g/dL for girls and boys, LLN value for local lab in Kenya 11.5 g/dL for girls and 14.5 g/dL for boys, Schellenberg reference 8.2-9.3 g/dL average anemic defined as <11.0 g/dL	Value simplified and adjusted for safety to 11.0 g/dL
Children 1-2 yrs	11.0		Schellenberg reference 8.0 g/dL average anemic defined as <11.0 g/dL, DMID toxicity table 11.0 g/dL	Value simplified and adjusted for safety to 11.0 g/dL

DMID US FDA Guidance Document Division of Microbiology and Infectious Diseases (DMID) Pediatric Toxicity Tables November 2007.

6. ICS CALCULATION

For each type of cytokine expressing T cells (CD4+ or CD8+), each peptide pool (GP1 or GP2) and both negative control, the database will contain:

- Total number of cells (*nsub*)
- Total cell count of cytokine expressing T cells (any of IL-2 or IFN- γ or TNF- α present)
- Marginal cytokine expressing T cells subsets (*cytnum*)

To calculate the background adjusted percentage of any subset (GP1 and GP2 combined) for the total cytokine response and the “*pure*” cytokine combinations (table below), the following steps should be followed:

Cytokine combinations			Formula for “pure” cytokine counts
IFN- γ	IL-2	TNF- α	
+	+	+	IFN- γ +IL-2+TNF- α +
-	+	+	(IL-2+TNF- α +) - (IFN- γ +IL-2+TNF- α +)
+	-	+	(IFN- γ +TNF- α +) - (IFN- γ +IL-2+TNF- α +)
+	+	-	(IFN- γ +IL-2+) - (IFN- γ +IL-2+TNF- α +)
-	-	+	(TNF- α +) - (IFN- γ +TNF- α +) - (IL-2+TNF- α +) + (IFN- γ +IL-2+TNF- α +)
-	+	-	(IL-2+) - (IFN- γ +IL-2+) - (IL-2+TNF- α +) + (IFN- γ +IL-2+TNF- α +)
+	-	-	(IFN- γ +) - (IFN- γ +IL-2+) - (IFN- γ +TNF- α +) + (IFN- γ +IL-2+TNF- α +)

1. Apply the formula from the table above with the marginal cytokine counts (*cytnum*) for each “*pure*” cytokine combination (*c_cytnum*)

Example: for IFN- γ - and IL-2+ and TNF- α +

$$C_{\text{cytnum}} = \text{cytnum}_{(\text{IL-2+TNF-}\alpha\text{+)}} - \text{cytnum}_{(\text{IFN-}\gamma\text{+IL-2+TNF-}\alpha\text{+)}} \quad (\text{Ex1})$$

For each cytokine combination apply the formula also for both negative controls (*c_cytnum_neg*).

2. Because we cannot link a specific negative control to a given peptide pool (GP1 or GP2), the average of the negative controls (*c_cytnum_neg*) will be used.

For each peptide pool (GP1 or GP2), calculate the background adjusted percentages (*c_pctpos_{adj_x}*) for each cytokine combination using the following formula:

For each GP_x ($x = 1$ or 2),

$$c_{\text{pctpos}_{\text{adj}_x}} = \left\{ \frac{c_{\text{cytnum}_x}}{nsub_x} - \frac{\text{mean}(c_{\text{cytnum}_\text{neg}})}{\text{mean}(nsub_\text{neg})} \right\} \times 100$$

Where *nsub_x* and *nsub_{neg}* are total number of cells for the cytokine assay and control assay respectively.

Note: If replicate negative control samples are available for a subject at one timepoint, only the ones belonging to the same assay as the antigens should be used in the above formula.

3. If the background adjusted percentage is negative, it should be set to 0. The total background adjusted “*pure*” percentage is the sum of the background adjusted percentages from peptide pools GP1 and GP2. It is expressed as

$$\text{Max}(\text{c_pctpos}_{\text{adj}_1}, 0) + \text{Max}(\text{c_pctpos}_{\text{adj}_2}, 0)$$

4. The total background adjusted “*pure*” percentages will be used for the pie charts.
5. The background adjusted total cytokine response is determined by Steps 2 and 3 above. They will be graphically displayed on the \log_{10} -scale and the original scale.
6. Excluded data points:

There are 2 reasons **to filter** data:

- High background: this is only captured on the records” IFN- γ + or IL2+”
- Total cell count (nsub) < 5000

In addition, a certain part of the data may be **unreliable**. If for a considered type of cytokine expressing T cells (CD4+ or CD8+), a part of the results from a sample or all the results from a sample are filtered or unreliable, the entire sample will be excluded from the analysis. That is, the background adjusted total cytokine response for the considered subject, T cell sample (CD4+ or CD8+) and time point is missing and the background adjusted percentages of the “*pure*” cytokine combinations are not displayed.

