6.2.2. Cellular Immune Responses

6.2.2.1. Parameters

Cellular immune responses, as measured by the following assays, will be analyzed:

- **ELISpot:** EBOV GP-specific IFN- γ producing T cells, measured as the number of spot-forming units per million peripheral blood mononuclear cells (SFU/10⁶ PBMC).

The following will be defined for ELISpot:

- **Sample interpretation:** Sample positivity (interpretation) will be determined for each of the peptide pools separately. If a sample is considered positive for at least one of the peptide pools, the sample is considered positive. A sample will be considered positive when the EBOV peptide pool-stimulated readout is greater than 3-fold the mock (unstimulated) readout and the mock-subtracted value is greater than the threshold. The threshold is assay-specific and will be provided by the vendor.
- **Responder:**

- If sample interpretation is negative at baseline but positive post-baseline and the post-baseline value is greater than $2 \times$ Threshold; OR
- If sample interpretation is positive at both baseline and post-baseline and there is a greater than 2-fold increase from baseline.

- **ICS:** The following responses will be measured:
 - CD4+: IL-2, IFN- γ , and/or TNF- α responses to EBOV GP.
 - CD8+: IL-2, IFN- γ and/or TNF- α responses to EBOV GP.

For each type of cytokine expressing T cell (CD4+ or CD8+), each peptide pool (GP1 or GP2) and both negative controls, the database contains the total cell count of cytokine expressing T cells and the marginal cytokine expressing T cells subsets (in the text below referred to as “*cytnum*”) and the total number of cells (*nsub*). For the computation of the background adjusted percentage for any peptide pool (GP1 and GP2 combined) for the total cytokine response and the “pure” cytokine combinations, see the detailed steps outlined in Attachment 6.

In addition, the following will be defined for the ICS:

- **Sample interpretation:** For each antigen, the total cytokine count of the considered antigen is compared with the total cytokine count in all negative control samples with the Fisher’s exact test (Table 5). The test is repeated for both peptide pools (GP1 and GP2) and for each antigen. If the observed p-value for at least 1 peptide pool (GP1 or GP2) is below $10^{-5}/2$ (division by 2 due to Bonferroni correction as this is done for each pool), the sample interpretation is considered positive for that antigen².

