Table 5: Generic Contingency Table for the Fisher’s Exact Test

	GP _x ($x = 1$ or 2)	Negative controls
Cells expressing cytokines	$cytnum_x$	$cytnum_neg1 + cytnum_neg2$ (or in case of 1 negative control: $cytnum_neg$)
Cells not expressing cytokines	$nsub_x - cytnum_x$	$(nsub_neg1 + nsub_neg2) - (cytnum_neg1 + cytnum_neg2)$ (or in case of 1 negative control: $nsub_neg - cytnum_neg$)

cytnum: marginal cytokine counts; *cytnum neg1*: cell counts of one negative control; *cytnum neg2*: cell counts for the other negative control; *nsub*: total number of cells for the cytokine assay; *nsub neg1*: total number of cells for one control assay; *cytnum neg2*: total number of cells for the other control assay. Note that a given negative control (ie, in case of 2 negative controls) cannot be linked to a specific peptide pool (GP1 nor GP2) because the necessary linking information will not be available in the database.

- **Responder:**
 - If sample interpretation is negative at baseline but positive post-baseline and the post-baseline value is greater than $2 \times$ LLOQ; OR
 - If sample interpretation is positive at both baseline and post-baseline and there is a greater than 2-fold increase from baseline in background adjusted total cytokine response.

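### ICS positivity is tested against all negative controls while ICS magnitude uses same-assay controls only, so where controls come from more than one assay a real response can be called negative

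*SAP*

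**What the plan says.** Two parts of the SAP define the background for an ICS sample.

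- **Magnitude (Attachment 6, Step 2).** The background-adjusted percentage for a peptide pool is the pool's cytokine-positive fraction minus mean control count over mean control cell number. The Note to this step reads: "If replicate negative control samples are available for a subject at one timepoint, only the ones belonging to the same assay as the antigens" may enter, and it limits its own reach to that formula: "only the ones belonging to the same assay as the antigens should be used in the above formula".
- **Positivity (Section 6.2.2.1).** By Fisher's exact test, "the total cytokine count of the considered antigen is compared with the total cytokine count in all negative control samples". Table 5 adds two negative controls together, or takes one if there is only one, with no condition on the assay they came from. Its footnote says only that a control cannot be matched to a pool: "Note that a given negative control (ie, in case of 2 negative controls) cannot be linked to a specific peptide pool".

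The cut-off is 10^-5 halved ("division by 2 due to Bonferroni correction as this is done for each pool"), and one positive pool makes the sample positive. Section 6.2.2.1 refers to Attachment 6 for computing percentages. Nothing carries the Note over to the test.

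Section 6.2.2.3 reports positivity and responder rates per time point with exact intervals, and restricts the ICS pie and bar charts to responders. Both responder rules require a positive post-baseline sample.

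**The concern.** The Note shows that the sponsor expects some subjects to have controls from another assay at the same time point, and does not regard them as valid background for the stimulated wells. The positivity test, as worded, still takes them in. The same well is then measured against one background and tested against another.

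If the other assay ran with a higher background, pooling its controls dilutes the contrast and a response that is plain within its own assay can miss the cut-off. If it ran lower, pooling can create a contrast that is absent within the assay. Positivity rates are at stake in both directions; responder rates and the responder-only charts are at stake in the first.

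**Working it through.** **Inputs from the SAP.** Per-pool cut-off 10^-5/2 = 5e-6 (Section 6.2.2.1); two pools at 5e-6 sum to 1e-5, so the stated split is reproduced. Negative adjusted values become zero ("If the background adjusted percentage is negative, it should be set to 0"). The only cell-count figure is an exclusion limit ("Total cell count (nsub) < 5000").

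**Assumed inputs.** Cell number per well (n) and background are not given. I took n from 20,000 to 500,000, equal across wells, and backgrounds of 0.02% to 0.20%. The examples concern one pool; the other is taken as not positive. The sidedness of the test is not stated: p-values are two-sided, and one-sided values give the same calls in every case shown.

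**Step 1: can the two rules disagree?** mean(count)/mean(n) = sum(count)/sum(n). With one and the same control set, the adjusted percentage and the Table 5 contrast always point the same way. A disagreement in direction requires different control sets, which is what the wording allows.

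**Step 2: lost response.** Stimulated well 0.10%, same-assay control 0.02%, other-assay control 0.10%. Adjusted response: 0.10 - 0.02 = 0.08%. For n = 50,000 and one control of each kind, the table changes from 50/50,000 vs 10/50,000 to 50/50,000 vs (10 + 50)/100,000.

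| n | Controls | p, same-assay only | p, all controls |
|---|---|---|---|
| 20,000 | 1 vs 1+1 | 0.0015 | 0.11 |
| 20,000 | 2 vs 2+2 | 5.4e-5 | 0.067 |
| 50,000 | 1 vs 1+1 | 1.6e-7 | 0.008 |
| 50,000 | 2 vs 2+2 | 1e-10 | 0.004 |
| 100,000 | 1 vs 1+1 | 5e-14 | 1.9e-4 |
| 100,000 | 2 vs 2+2 | 5e-20 | 3.3e-5 |
| 200,000 | 1 vs 1+1 | 9e-27 | 1.6e-7 |
| 200,000 | 2 vs 2+2 | 1e-38 | 5.3e-9 |

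At 50,000 and 100,000 cells the call changes from positive to negative. At 20,000 the sample is negative either way, and at 200,000 positive either way. If the other assay's control is at 0.15%, the positive is still lost at 500,000 (p = 0.0016 with 2+2, 0.0042 with 1+1).

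**Step 3: positive call at zero response.** Stimulated well 0.10%, same-assay control 0.10%, so the adjusted response is 0 and the same-assay p is 1. Pooled p:

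| n | Other-assay control | 1+1 | 2+2 |
|---|---|---|---|
| 50,000 | 0.02% | 0.008 | 0.004 |
| 100,000 | 0.02% | 1.9e-4 | 3.3e-5 |
| 200,000 | 0.02% | 1.6e-7 | 5.3e-9 |
| 200,000 | 0.05% | 0.002 | 5.5e-4 |
| 500,000 | 0.05% | 8.2e-7 | 5.5e-8 |

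A five-fold gap needs about 200,000 cells and a two-fold gap about 500,000. Higher backgrounds lower the requirement: 0.20% against 0.05% crosses at 100,000 (1.1e-6 and 6.1e-8).

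The five-fold rows equal the pooled column in Step 2 because the pooled tables are identical. The test on all controls cannot tell a 0.08% response from none.

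**Step 4: responder status.** A lost post-baseline positive fails both responder rules, so the subject is a non-responder and leaves the charts. A post-baseline false positive with adjusted value 0 cannot exceed 2 x LLOQ or rise more than two-fold. For a baseline false positive with adjusted value 0, Section 6.2.2.2 sets values below LLOQ to LLOQ in fold increases, so a rise above two-fold means a value above 2 x LLOQ: the two rules coincide.

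**The case against.** The best defence is context. The SAP speaks of both negative controls, Table 5 holds at most two, and its footnote is about matching controls to pools. Read that way, testing against all controls may only mean adding the usual pair, and a programmer could assume that the pair shares an assay. This does not settle it: one same-assay and one other-assay control fit Table 5 exactly, and the 1+1 rows show the same errors. Two programmers could code the rule differently.

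Other limits stand. The Note is conditional, and the SAP does not say how often controls from another assay occur. Attachment 6 removes high-background data and drops the whole sample if any part is filtered; with no limit stated, this may or may not catch the samples that matter. ICS is exploratory and confined to the PBMC subset (targets of 165 in Cohort 1 and 33 in each other cohort).

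Two stronger readings are tempting and not supported. A reader might infer that ordinary background differences produce false positives at any realistic cell count; at a five-fold gap (0.10% against 0.02%) none appeared at 50,000 or 100,000 cells. A reader might also infer that a false positive at baseline alters who is a responder by switching the rule; with zero adjusted response it does not, by the LLOQ imputation in Section 6.2.2.2.

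**Conclusion.** The inconsistency is real, and the positivity rule as written can give a wrong call where controls come from more than one assay. The main risk is a lost response: at assumed counts of 50,000 to 100,000 cells and a five-fold higher background in the other assay, a clear positive becomes negative, and after baseline a responder can be lost with it. The reverse error is harder to reach and affects only the positive-sample rate.

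The size rests on assumed cell counts and backgrounds, and the number of affected samples is unknown. Primary and secondary endpoints are untouched. This is a minor correction, worth making because the sponsor's own rule already supplies the answer.

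**What to change.** In SAP Section 6.2.2.1 (ICS sample interpretation) and in the negative-control column of Table 5, add the condition that the controls must belong to the same assay as the antigens, in line with the Attachment 6 Note. Magnitude and positivity then rest on one background: in the examples above, the 0.08% response is positive from 50,000 cells upward and the zero response has p = 1.

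The cost is one phrase and no new data. Where only one same-assay control remains, the test has fewer control cells; Table 5 already provides for that case, and the lost-response example stays positive with one control at 50,000 cells (1.6e-7).
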